### **10.3 Risks and Discomforts**

#### **10.3.1 Related to dexamethasone**

The side-effects of topical steroids are usually limited to Candida (yeast) infection. This is relatively uncommon in our subject population (<5%), easily treatable and does not require discontinuation of the prophylaxis.

Low levels of topical steroids are absorbed through the oral mucosa, but the exact rate is not known. Possible risks associated with absorbed drug include:

- Adrenal suppression: While adrenal suppression is very rare with topically applied corticosteroids, it is physiologically possible. Cases of adrenal suppression following topically-applied steroid creams have been reported with long-term use on extensive body surface primarily in young children. In other reports, it was difficult to determine if there was true adrenal suppression. Symptoms of adrenal suppression are non-specific and include fatigue, nausea and abdominal discomfort. Since these symptoms are extremely common in the general hospital population, routine monitoring in the context of this study is not indicated. In this study, blood pressure will be monitored at every visit, and adrenal function will be assessed at the end of prophylaxis. Given the very short duration of this study, we do not expect significant side effects.

In the unlikely event of significant adrenal suppression as assessed by repeat ACTH stimulation test, Clinical Center Endocrinology Service will be consulted (see section 8.4.6, Assessment of Adrenocortical Function [Cortisol] levels).

- Growth and bone health: Impairment of childhood growth with an approximate cortisone dose of 1.5 mg/kg/day was first described over 40 years ago; osteopenia in children receiving a prednisolone dose of less than 0.16 mg/kg/day has also been reported. Loss of bone and deterioration in short term growth are dependent on the type and dose of glucocorticoid and occur most prominently over the first six months of treatment.

We will monitor pre-pubertal pediatric subjects by use of growth chart (length for age, weight for age percentiles and body mass index for age percentiles) and bone age (hand x-ray) if the results are available on the parent transplant protocol.

- Acute tumor lysis: Two cases of acute tumor lysis syndrome in patients with acute leukemia have been reported in the literature following dexamethasone for prophylaxis of peri-operative nausea and vomiting; one of which was fatal (patient had a new onset of undiagnosed acute leukemia). Although the dexamethasone on this study is administered as an oral rinse (not swallowed), low levels (exact rate unknown) of topical steroids are absorbed through the oral mucosa. Although it is very unlikely that acute tumor lysis would occur in our study, in the event of disease relapse in leukemia subjects, the study drug will be stopped, and the subject will go off-study (see section 8.8.2)

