## 2.4 GVHD Therapy

### 2.4.1 Systemic immunosuppressive agents

The treatment for GVHD consists of various systemic immunosuppressive agents, most commonly systemic corticosteroids, cyclosporine, tacrolimus, mycophenolate, and sirolimus. Long-term immunosuppressive treatment for GVHD has a variety of serious side effects including life-threatening infections, aseptic bone necrosis, hypertension, and secondary diabetes [3, 19].

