## **2.5 Scientific and Clinical Justification**

Prevention of oral GVHD by topical agents is an attractive strategy because it would potentially avoid the adverse effects associated with systemic immunosuppression. Most importantly, using immunosuppressive and tolerizing agents locally would concentrate the effects in the area where they are beneficial, as GVHD occurs in response to recognition of peripheral antigens by activated donor T-cells. Conversely, use of systemic agents for the same purpose would interfere not only with the undesirable GVH response, but also with immune responses directed against the malignancy (i.e. the graft vs. tumor effect), which is the principal mechanism through which reduced intensity transplants achieve sustained disease remission.

There are no studies of dexamethasone absorption when used topically in the oral cavity and expectorated. The systemic effects of topically administered dexamethasone solution have not been investigated. Since this is a commonly used agent for the treatment of oral inflammatory conditions including GVHD, knowledge of the degree of systemic action would be valuable. If the absorption is significant, some degree of adrenal suppression is likely. This may have implications in many situations when systemic effects of steroids are undesirable.

We therefore propose a trial of topical dexamethasone solution for prevention of chronic oral GVHD in stem cell transplant recipients ages 12 and older. Additionally, this study will provide valuable insights into the cellular and molecular alterations associated with the development of chronic GVHD and treatment with topical corticosteroids. This will lead to better understanding of the pathogenesis of chronic GVHD and potentially development of new therapeutic interventions.

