### **6.3 End of Treatment Monitoring and Assessments (3 months)**

Subjects will be evaluated at the NIH at 3 months (+/- 7 days) after starting study medication with the following assessments:

- Interim assessment
- Blood pressure
- Concomitant meds (immunosuppressive, antimicrobial and analgesics)
- The 0-10 Scale for Oral Pain (see Appendix A)
- The 0-10 Scale for Oral Xerostomia (see Appendix A)
- Patient-assessed Global Scale (perception of changes in oral condition-Appendix A)
- GVHD Severity Scale (see Appendix B)
- Lichen Planus (oral GVHD) Severity Scale (see Appendix C)
- Disease specific QOL- OHIP-14 scale (ages 18 and older only) (Appendix D)
- Complete blood count (CBC with diff) – done concurrently with post transplant monitoring
- Serum chemistry (Acute Care (Na, K, Cl, CO2, Creatinine, Glucose, and Urea Nitrogen), Mineral (Phosphorus, Magnesium, Albumin, and Calcium), Hepatic (Alk Phosphatase, ALT, AST, Total Bilirubin, and Direct Bilirubin), and Other (Total Protein, CK, Uric Acid, and LD) panel) – done concurrently with post transplant monitoring
- Serum cortisol level (results blinded to investigators)
- ACTH stimulation test (Optional)
- Serum dexamethasone level (results blinded to the investigators)
- Buccal mucosal less than approximately 6mm punch biopsy ages 18 and older only (optional)
- Oral photographs (Optional)
- Oral lesion documentation
- Research blood sample collection
- Saliva sample collection
- Growth chart (length for age, weight for age percentiles and body mass index for age percentiles, pre-pubertal children) (if hand x-ray is available on parent transplant protocol, the results will be reviewed)

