### **8.8.2 Principal investigator decision:**

Subjects will be taken off study during the 3 month study drug administration period:

- if they develop oral chronic GVHD in the period between baseline assessments and first dose of study drug (subjects will be reassessed between post-transplant days 90 and 100 to ensure absence of oral chronic GVHD and reinforce protocol procedures)
- if they are unable to comply with the study visits or become severely ill and cannot comply with the intervention
- if they reach the primary endpoint of clinically significant oral chronic GVHD
- if they have relapse of their underlying disease (leukemia subjects, see section 10.3.1 risk of tumor lysis)

These subjects will be asked to complete the required off study drug evaluations and end of study assessments.

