### 9.2 Adverse Events

Because dexamethasone is an FDA approved drug with known toxicity profile, any observed or volunteered adverse events will not be captured in the database unless (1) the adverse event is previously unknown (not on the label) or more severe than on the label and deemed possibly, probably or definitely related to the study medication or (2) meets the criteria for a severe adverse event. Adverse events that are complications of the primary transplant protocol and deemed unlikely or unrelated to dexamethasone will not be captured in the database for this protocol, but will be collected and reported in the transplant protocol. The collection of AE information will begin on the first day of initiation of the study drug.

The NCI Common Terminology Criteria for Adverse Events Version 4 (CTCAE) will be used for toxicity and adverse event reporting. All appropriate treatment areas have access to a copy of the CTCAE version 4.0. A copy of the CTCAE version 4.0 can be downloaded from the CTEP web site (<http://ctep.cancer.gov>).

**Adverse event** is defined according to 21 (CFR 312.32(a)) as any untoward medical occurrence associated with the use of a drug in humans, whether or not considered drug related. An adverse event can also be any unfavorable and unintended diagnosis, symptom, sign (including an abnormal laboratory finding), syndrome, or disease temporally associated with the use of a drug, without any judgment about causality. Adverse event either occurs during the study participation, having been absent at baseline or if present at baseline, appears to worsen.

An abnormal laboratory value will be considered an AE if the laboratory abnormality is characterized by any of the following:

- Results in discontinuation from the study
- Is associated with clinical signs or symptoms
- Requires treatment or any other therapeutic intervention
- Is associated with death or another serious adverse event, including hospitalization
- Is judged by the Investigator to be of significant clinical impact
- If any abnormal laboratory result is considered clinically significant, the investigator will provide details about the action taken with respect to the test drug and about the patient's outcome.

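### The by-arm adverse event table in 8.5 omits infections and relapses judged to be transplant complications, because 9.2 and 9.3 filter capture by labelling and attribution

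*Combined protocol and SAP*

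**What the plan says.** Safety stands beside efficacy in the primary objective (1.1, 8.3). The relevant statements are these.

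- **Harms of systemic treatment.** Section 2.4.1 states: "Long-term immunosuppressive treatment for GVHD has a variety of serious side effects including life-threatening infections". Its paragraph on systemic corticosteroids also reports more infections. Section 2.5 argues that systemic agents interfere with the undesirable graft-versus-host response "but also with immune responses directed against the malignancy (i.e. the graft vs. tumor effect", which it presents as the main route to lasting remission after reduced-intensity transplant.
- **Risks of the rinse.** Section 10.3.1 opens with "The side-effects of topical steroids are usually limited to Candida (yeast) infection". Under "Possible risks associated with absorbed drug include" it lists adrenal suppression, growth and bone health, and acute tumor lysis. Relapse appears only as a trigger for action: "in the event of disease relapse in leukemia subjects, the study drug will be stopped, and the subject will go off-study".
- **Exposure.** Sections 2.5 and 10.3.1 say absorption through the mouth is unstudied or of unknown rate. Section 5.1.1 gives about 20 mg/day of prednisone equivalent if every dose is swallowed.
- **Analysis.** Section 8.5 plans a table of adverse events by severity and treatment arm.
- **Capture.** Section 9.2 records an event only if it is off-label or worse than the label and at least possibly related, or if it meets the severe-event criteria. It adds: "Adverse events that are complications of the primary transplant protocol and deemed unlikely or unrelated to dexamethasone will not be captured in the database". Section 9.3 reports on this study only serious events judged at least possibly related.
- **Related records.** Section 6.3 lists "Concomitant meds (immunosuppressive, antimicrobial and analgesics"; 6.2 and 6.5 have similar items. Section 8.8.2 takes subjects off study during the drug period "if they have relapse of their underlying disease", with a parenthesis referring to leukemia subjects.

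**The concern.** The case for a topical agent is that it should spare patients the harms of systemic immunosuppression. Whether it does so depends on how much drug is absorbed, which nobody knows. Infection and loss of anti-tumor effect are therefore the natural harms to count in both arms.

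In recipients starting the rinse 90 to 100 days after transplant, these are also events that an investigator can readily put down to the transplant. Under 9.2 and 9.3, events attributed that way leave this study's data and go to the parent protocol. A randomised placebo group removes the need to judge causality case by case, and the filter gives that advantage away. The trial could report a clean safety table while most infections and relapses in either arm were never in it.

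**Working it through.** **1. The plan's own figures.** Inputs from 8.2: 36 per arm, 15% vs 45%, significance level 0.05 (taken as two-sided). With pooled variance and no continuity correction,

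power = Φ{[|p1−p2|√n − 1.96√(2p̄q̄)] / √(p1q1+p2q2)}

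= Φ{[1.800 − 1.270] / 0.612} = Φ(0.865) = 80.7%.

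The stated 80% reproduces. For exposure, 11.1 gives 1 mg per dose and 0.75 mg dexamethasone ≈ 5 mg prednisone. With three doses a day, 3 × 1 × 5/0.75 = 20 mg/day, as 5.1.1 says. This is an upper bound, since subjects are to expectorate.

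**2. What reaches the 8.5 table.**

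| Event | Judged at least possibly related | Judged a transplant complication, unlikely or unrelated |
|---|---|---|
| Infection, on label and not severe | Not captured (9.2) | Not captured (9.2) |
| Severe or serious infection | Captured | Excluded by the last clause of 9.2 and by 9.3 |
| Relapse | Captured if off-label or severe | Excluded; seen only as an 8.8.2 off-study reason |

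Nothing in 8.4 or 8.5 analyses infection or relapse separately.

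**3. Whether existing records can replace it.** Sections 6.2, 6.3 and 6.5 ask about antimicrobial use but specify neither indication nor start date. Every subject is placed on clotrimazole prophylaxis (5.2.1), and 2.4.2 says most patients already receive preventive antifungals. Use therefore does not identify infection. The 8.8.2 relapse reason carries a leukemia qualifier, so recording in other diseases is uncertain.

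**4. Why simple month-3 proportions would mislead.** Subjects reaching the primary endpoint leave the study (5.3, 8.5, 8.8.2). At the planning rates, 36 × 0.45 = 16.2 would leave on placebo and 36 × 0.15 = 5.4 on dexamethasone. Assume for illustration that they leave evenly over three months:

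- placebo: (36 − 16.2/2) × 3 = 27.9 × 3 = 83.7 person-months;
- dexamethasone: (36 − 5.4/2) × 3 = 33.3 × 3 = 99.9 person-months.

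With identical true rates, dexamethasone would show about 99.9/83.7 = 1.19 times as many events. The distortion shrinks if most endpoints are found at the month-3 visit.

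**5. Precision with full capture.** Event rates here are assumed; the documents give none. The 95% half-width for a difference is 1.96√[(p1q1+p2q2)/36]:

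- 10% vs 20%: 1.96√[(0.09+0.16)/36] = 0.163;
- 30% vs 50%: 1.96√[(0.21+0.25)/36] = 0.222.

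Power by the formula in step 1:

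| Control rate | 10-point excess | 20-point excess | 30-point excess |
|---|---|---|---|
| 10% | 22% | 57% | 85% |
| 20% | 16% | 46% | 77% |
| 30% | 14% | 41% | 73% |

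**The case against.** Several objections have force.

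- **A by-arm safety table exists.** A reader might infer that no by-arm comparison is planned. Section 8.5 contradicts that. Severe or serious events judged at least possibly related would appear in it, so it is also too strong to say that the trial cannot cover these harms. What remains is that the table is selectively fed.
- **Blinding protects attribution.** Investigators do not know the arm (4.3, 5.1), so the filter should not favour one side through knowledge of treatment. This stands against bias. It does not bring back discarded events.
- **Infection is mentioned.** Section 10.3.1 names oral Candida, so only systemic infection is missing. The list is introduced by a word that does not claim completeness.
- **Relapse is an inference.** Section 2.5 speaks of the graft-versus-tumor effect, not of relapse as a harm of the drug. The step is short, but it is the reader's.
- **The data may seem to be in hand.** A reader might infer that the medication queries and off-study reasons already supply both outcomes whatever the attribution. The documents do not support this: antimicrobial use has no indication attached, and relapse carries the leukemia qualifier.
- **The sample is small.** This is true, and it limits the tables to description. It is a reason to show the uncertainty, not to leave the events uncounted.

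**Conclusion.** The point holds as a matter of capture. The 8.5 table would show infection and relapse only to the extent that investigators attributed them to the study drug, although the protocol's own rationale makes them the harms to watch and absorption is unknown. A favourable safety statement would not rest on a full randomised count of either.

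The number of events lost cannot be stated, because the documents give no infection or relapse rate and no attribution rate. The conclusion assumes that a sizeable share would be attributed to the transplant, which is plausible in this population but not demonstrated.

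Full capture would not make the trial decisive. On the assumed rates, power for a 10-point excess is 14% to 22%, and the intervals span roughly 16 to 22 points either side. The gain is an unfiltered description by arm. The change is worth making; the primary efficacy analysis is unaffected.

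**What to change.** Add to 8.5 two descriptive safety tables by randomised arm, regardless of attribution, each with a 95% confidence interval for the difference:

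1. **Infection:** new antimicrobial started to treat infection after first dose, with oral antifungal treatment shown separately. Add indication (treatment or prophylaxis) and start date to the medication record in 6.2, 6.3 and 6.5.
2. **Relapse:** relapse of any underlying disease during the three-month drug period. Record it under 8.8.2 for all subjects, not only those with leukemia. This concerns recording and changes no rule on who stops treatment.

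Report events per person-time from first dose to month 3 or going off study, and state the denominators. Use parent transplant protocol records to month 3 where available. Person-time corrects for unequal follow-up but not for any link between leaving and the risk of these events, so the tables should say so.

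Exempt these two event types from the 9.2 and 9.3 attribution and labelling filters for these tables. Reconcile the absorbed-drug list in 10.3.1 with 2.4.1 and 2.5.

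The cost is two tables, two fields on the medication record, and some retrieval of parent-protocol records. No new visit or sample is needed. The intervals will be wide, and the plan should say in advance that the tables cannot rule out a moderate excess.

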### **5.4.2 *Adrenal suppression***

Asymptomatic subjects without clinical signs of adrenal insufficiency and abnormal ACTH and/or cortisol test results at the end of the intervention period may be observed without steroid replacement and retested in 1 month. In case of development of symptoms suggestive of adrenal suppression (such as abdominal pain, nausea and vomiting, fatigue and hypotension) subjects will then be placed on the standard maintenance replacement regimen of the corticosteroids such prednisone 5-7.5 mg once daily and reevaluated in 1 month

by ACTH testing. All subjects with the abnormal ACTH test results will be advised of the symptoms and signs of clinically significant adrenal suppression and will be given stress doses of hydrocortisone injections for emergencies and a wrist bracelet.

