### **6.2 On Study Drug Interim Assessments (1 month and 2 month phone contact)**

The NIH research team will contact the subject by clinical appointment, telephone or email at 1 month and 2 months (+/- 2 weeks) after initiation of study drug to inquire about adverse effects and the use of concurrent medications. Laboratory assessments done as part of their post transplant monitoring will also be reviewed when available. Subjects will be asked to return to clinic when clinically indicated and the following questionnaires will be completed at the time of contact.

- Concomitant meds (immunosuppressive, antimicrobial and analgesics)
- The 0-10 Scale for Oral Pain (see Appendix A)
- The 0-10 Scale for Oral Xerostomia (see Appendix A)
- Patient-assessed Global Scale (perception of changes in oral condition)

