### **6.4 Follow-up Remote Assessment**

If available, after completion of study drug, subjects will be contacted by clinic appointment, phone or email monthly +/- 2 weeks for 5 months: Months 4, 5, 6, 7, and 8. Subjects will be asked to report any symptoms or signs consistent with oral chronic GVHD. In addition, the monthly follow-up remote visits will be used to confirm the absence of oral chronic GVHD symptoms (oral discomfort and xerostomia) and collect the information about the current use of medications. If subject reports symptoms or signs consistent with oral

chronic GVHD, the following will be performed at the time of contact:

- Concomitant meds (immunosuppressive, antimicrobial and analgesics)
- The 0-10 Scale for Oral Pain (see Appendix A)
- The 0-10 Scale for Oral Xerostomia (see Appendix A)
- Patient-assessed Global Scale (perception of changes in oral condition)

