#### 8.4.6 Assessment of adrenocortical function (cortisol levels)

Subjects will be evaluated for possible hypothalamic-pituitary axis (HPA) axis suppression with the following measures:

1. Morning cortisol levels will be determined at baseline, monthly follow-ups (done at NIH), and at completion of the interventional phase (3 months after the last dose of study medication). The results will be blinded to the investigators until the end of the study. At the end of the study, in subjects with morning cortisol levels between 19 mcg/dL and 3 mcg/dL no further adrenal function testing will be performed.
2. In subjects with the symptoms of suspected adrenal insufficiency, a Short Cosynthropicin Test (SCT) will be performed to determine if the subject has HPA axis suppression. In brief: venous blood will be collected before administration of 250 mcg of cosyntropicin (synthetic ACTH) around 8 AM to 12 noon, and at 30 and 60 minutes after. The expected rise in cortisol levels is to at least 18 mcg/dL (24). In cases of minimally abnormal SCT (stimulated cortisol values of 13-17 mcg/dL), the test will be repeated the next day, as it has been demonstrated that the result is often normal with a repeat test. This test has been shown to be sensitive and specific for evaluation of subclinical adrenal suppression [52, 53]. In the unlikely event of significant adrenal suppression as assessed by repeat ACTH stimulation test, Clinical Center Endocrinology Service will be consulted. Pharmacy will be requested to unblind therapy to the endocrinologist so that appropriate therapy can be initiated and the endocrinologist can appropriately attribute the relationship of the event to study drug administration.
3. The confounding effect of systemic corticosteroids will be taken into account at the time of analysis. We expect to have a subgroup of subjects who will not receive systemic steroids. This subgroup will be used to evaluate the effects of topical dexamethasone on adrenal secretion.

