### 8.5 Data Analyses

This study will be analyzed according to the “intent to treat” principle, that is, all randomized subjects will be included. Subjects not evaluated for endpoints will be considered to have reached the primary endpoint. Every effort will be made to reach and evaluate the subjects at the monthly intervals and at the end of the 3 month intervention period. The differences in proportions of significant oral chronic GVHD will be assessed by a chi-squared test (with continuity correction). Treatment group differences in the severity scores, pain and xerostomia scores, and quality of life scores (OHIP-14) will be assessed using the Wilcoxon test. Adjustments will be made for age and other covariates of interest, such as systemic immunosuppression. Adverse events will be tabulated by severity and treatment assignment. For pediatric subjects, analyses will include growth assessment (growth chart [length for age, weight for age percentiles

and body mass index] for age percentiles) and bone age and the associated z-scores (the number of standard deviations the child's measures [weight, height etc] differ from the population mean).

The intervention period will be 3 months. Should the subject reach the primary endpoint (development of clinically significant oral chronic GVHD), the subject will be asked to participate in end of study assessments and then will go off study. Subjects who did not develop oral chronic GVHD in the intervention phase of the study will be followed for up to 6 months to document late development of oral chronic GVHD. All subjects will be evaluated after 6 months after completion of the intervention phase of the study in the absence of clinical oral GVHD. Final statistical analysis will be performed once all subjects in the sample have completed the study and all records have been collected. We will use stratified analyses to account for effects of systemic immunosuppressive agents and other prognostic factors.

In the event of a protocol violation, the aggregate data will be analyzed with and without those subjects involved in the incident.

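### Section 10.3.1 declines to monitor common adrenal-type symptoms and 9.2 filters out most non-severe events, so the trial will have no systematic by-arm rate of non-severe systemic symptoms

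*Combined protocol and SAP*

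**What the plan says.** Section 1.1 makes safety part of the primary objective. Section 10.3.1 lists fatigue, nausea and abdominal discomfort as non-specific symptoms of adrenal suppression and continues: "Since these symptoms are extremely common in the general hospital population, routine monitoring in the context of this study is not indicated". It relies instead on blood pressure at visits and an assessment of adrenal function at the end of prophylaxis.

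Section 6.2 has staff contact subjects at months 1 and 2 "to inquire about adverse effects and the use of concurrent medications". What is then recorded is governed by 9.2, under which "any observed or volunteered adverse events will not be captured in the database unless" one of two conditions is met: the event is unlabelled or worse than labelled and judged at least possibly related, or it is severe. Complications of the transplant protocol judged unlikely or unrelated "will not be captured in the database for this protocol, but will be collected and reported in the transplant protocol". Section 8.5 plans that "Adverse events will be tabulated by severity and treatment assignment".

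The same symptoms have a clinical role. Section 8.4.6, item 2: "In subjects with the symptoms of suspected adrenal insufficiency, a Short Cosynthropicin Test (SCT) will be performed". In 5.4.2, symptoms lead to steroid replacement in subjects whose ACTH or cortisol result was already abnormal. Cortisol results are blinded until the end of the study (8.4.6), and the month-3 ACTH test is optional (6.3). After the drug stops, the monthly contacts in 6.4 turn to the mouth and to medications: "Subjects will be asked to report any symptoms or signs consistent with oral chronic GVHD".

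**The concern.** That a symptom is common in hospital patients makes it hard to attribute in one person. It does not make it uninformative in a blinded, 1:1, placebo-controlled comparison, where both arms share the same background. Individual attribution is especially weak here. All subjects are recent transplant recipients, and both arms receive clotrimazole, for which 10.3.2 lists nausea and vomiting. Yet for non-severe events 9.2 uses an individual relatedness judgement as the gate.

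Two things are at stake. First, the clinical side of the safety objective would rest on a general question followed by labelling, severity and attribution filters. The 8.5 table would show a selected subset and could be misread as a symptom profile. Second, the decision to order a cosyntropin test depends on symptoms that staff need not elicit in the same way from every subject, at a time when they cannot see the cortisol results.

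**Working it through.** **Can the 8.5 table contain these symptoms?** Take a subject who reports non-severe fatigue at month 1.

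1. It may be heard, because 6.2 asks about adverse effects. No visit list in 6.1 to 6.5 names fatigue, nausea or abdominal discomfort.
2. If it is on the label at that severity, neither condition in 9.2 is met and it is not recorded.
3. If it is not on the label, it is recorded only if judged at least possibly related. (The label is not in the documents, so both branches are shown.)
4. If it is seen as a transplant complication and judged unlikely or unrelated, it goes to the parent protocol. These documents describe no link from those records to treatment arm.
5. Section 9.2 says severe where 9.3 defines serious. If serious is meant, fewer events still are captured.

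So the table in 8.5 cannot give an unfiltered rate by arm.

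**Plan's own sample size.** Section 8.2: 15% versus 45%, 80% power, level 0.05. Two-sided pooled formula without continuity correction: [1.960 × √(2 × 0.30 × 0.70) + 0.842 × √(0.45 × 0.55 + 0.15 × 0.85)]² / 0.30² = (1.270 + 0.515)² / 0.09 = 35.4, that is 36 per arm. The figure reproduces, with power 80.7%, and n = 36 is used below.

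**What a symptom list could show.** The documents give no background rate. Assume that 20 to 50% of placebo subjects report a given symptom at least once in months 1 to 3.

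- Half-width of the 95% interval with equal rates p: 1.96 × √(2p(1 − p)/36). At p = 0.20 this is 1.96 × 0.0943 = 0.185.
- Power for excess d over background p0, with p1 = p0 + d and p̄ the mean of the two: Φ{[d√36 − 1.96√(2p̄(1 − p̄))] / √(p0(1 − p0) + p1(1 − p1))}. For 20% versus 40%: (1.200 − 1.270)/0.632 = −0.111, giving 45.6%.

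| Background | Half-width (points) | Power, +10 | Power, +20 | Power, +30 | Excess for 80% power (points) |
|---|---|---|---|---|---|
| 20% | 18.5 | 16.3% | 45.6% | 77.2% | 31.1 |
| 30% | 21.2 | 14.3% | 40.8% | 73.5% | 32.4 |
| 40% | 22.6 | 13.5% | 39.4% | 73.5% | 32.2 |
| 50% | 23.1 | 13.5% | 40.8% | 77.2% | 30.9 |

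Only a large excess could be seen.

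**Why not extend the by-arm comparison.** Subjects who reach the endpoint go off study. At the rates in 8.2, month 4 would keep about 36 × 0.55 = 19.8 placebo and 36 × 0.85 = 30.6 dexamethasone subjects. With 20 versus 31, the half-width is 22.5 to 28.1 points, in groups selected by outcome. For subjects not on systemic steroids the plan gives no number. If there were 12 to 24 per arm, the half-width would be about 23 to 40 points.

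**Why not test everyone who answers yes.** Using the three symptoms in 10.3.1 and the same assumed rates: if the symptoms overlap completely, 72 × 0.20 = 14.4 to 72 × 0.50 = 36 subjects would be sent for cosyntropin testing. If they are independent, the share is 1 − (1 − p)³ = 0.488 to 0.875, or 35.1 to 63.0 of 72.

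**The case against.** The case for the plan is substantial. Dexamethasone is an approved drug with a known toxicity profile, the trial calls itself a pilot, and selective capture is a stated choice. Adrenal suppression is described as very rare with topical use, and the plan prefers specific measures (blood pressure, cortisol, drug level) to non-specific complaints. Routine monitoring in 10.3.1 might even mean routine adrenal testing rather than symptom enquiry. A list that needs an excess of about 31 to 32 points for 80% power will settle little.

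Much of this stands. The laboratory measures are the better evidence on adrenal function, and the list is descriptive only. What does not stand is the reason given in 10.3.1, and under either reading of that sentence 9.2 produces the same gap.

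Some stronger readings are tempting, and the documents do not support them:

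- *No non-severe symptom is compared by arm.* Oral pain and xerostomia are scored at baseline, months 1, 2 and 3 and end of study, and OHIP-14 is collected in adults. Section 8.5 compares all three by arm.
- *Nobody asks about adverse effects.* Section 6.2 does, so the main loss is in recording.
- *Adrenal effects go unmeasured.* Cortisol is taken at baseline and month 3, plus any follow-ups done at NIH. The dexamethasone level is taken at month 3, and blood pressure is listed at screening, month 3 and end of study.
- *Symptoms alone start steroid replacement.* In 5.4.2 they act after an abnormal test. Every subject with an abnormal ACTH result is also told the warning signs and given emergency hydrocortisone.
- *The parent protocols cannot be linked to arm.* They are not in these documents. One can say only that no link is planned here.

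**Conclusion.** The point holds for non-severe systemic symptoms: this trial's database will contain no systematic by-arm rate of fatigue, nausea or abdominal discomfort. That follows from two stated rules, in 10.3.1 and 9.2, and rests on no assumed figure. The value of closing the gap does rest on assumptions. With 36 per arm and background rates of 20 to 50%, the interval for each symptom is about plus or minus 18 to 23 points, and power for a 20-point excess is 39 to 46%. A reader should not infer that a list would establish safety or exclude a moderate excess. The gain is an unfiltered descriptive estimate, and the same symptom information for every subject when a clinician decides on a cosyntropin test. Grade: consider, as a cheap improvement.

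**What to change.** - **10.3.1 and the visit lists.** Replace the sentence that declines monitoring with a short fixed yes/no list of what patients can report: fatigue, nausea, vomiting, abdominal pain or discomfort. Ask it identically in both arms at baseline and months 1, 2 and 3, or at the early end-of-study assessment for subjects who leave before month 3. Leave hypotension to measured blood pressure.
- **After the drug stops.** Ask the list once more at the first contact, for individual clinical use only.
- **9.2.** Exempt the list from the capture filter.
- **8.5.** Add one descriptive table for months 1 to 3 in all randomised subjects: each symptom by arm with the difference, 95% interval and the number asked, beside cortisol and blood pressure. Make no hypothesis test. Add a note on multiplicity: with four symptoms and no drug effect, the chance that at least one interval excludes zero is 1 − 0.95⁴ = 18.5% if they were independent. Also note that dexamethasone is used against nausea (10.3.1, on tumour lysis), so a null nausea difference could hide opposing effects.
- **Do not add** by-arm tables for month 4 or for subjects not on systemic steroids. Both groups are open to selection after randomisation, and both are too imprecise.
- **8.4.6.** Keep cosyntropin testing on clinical suspicion, informed by the list.

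The cost is a few questions at contacts already scheduled, one table, and possibly some extra for-cause tests. Subjects who reach the endpoint early will have been asked fewer times, and the denominators should make that visible.
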